 - If individual not currently enrolled in mental health treatment decides to enroll in such then he/she may become eligible to participate in the study.
 - If individual enrolled in mental health treatment schedules and attends a mental health visit then he/she may become eligible to participate in the study
- 5) Agrees to remain in mental health treatment throughout the duration of the study.
- 6) Can adequately care for and handle the dog.
 - Adequately caring for a dog requires that participants will be responsible for and able to provide food, water, protection, shelter, exercise, transportation, and treatment related to their assigned dog.
 - Adequately handling the dog means having the ability to give and reinforce obedience commands and control the dog using a leash.
- 7) Home environment is suitable for a dog.
 - If the home environment can be remedied the individual may become eligible to participate in the study.
 - If a participant moves home while enrolled in the study the new home must be suitable for a dog.
- 8) Home environment is structurally and geographically accessible to study staff.
 - If the home is geographically inaccessible to study staff and, the individual cannot remedy the situation unless he/she moves home. The study team will not encourage this. If a move takes place, it will be the individual's responsibility to re-contact the study team.
 - If the individual changes home residence while enrolled in the study, the new home must be geographically accessible to study staff. If it is inaccessible, the dog will be removed and the individual will be withdrawn from the study.
- 9) Is willing to accept randomization outcome.
- 10) Has someone to care for the dog during extended absence of the participant.
 - If no one is available to care for the dog but the situation changes then the participant may become eligible to participate.
- 11) Others in home are agreeable to having dog.
 - If others in the home are not agreeable but at a later date the situation changes, then the potential participant may become eligible to participate
- 12) Is willing and able to travel (by air or car) to the dog vendor training site for pairing if assigned to receive a service dog.
 - If individual's unwillingness to travel to a training site changes, he/she may become eligible to participate. In this instance, it will be the individual's responsibility to re-contact the study team.

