 - After a total of 10 dogs have been placed with participants who have children between the ages of 5 and 10 years, and after each pairing has successfully reached and passed the 2-month home visit, this exclusion criterion will be revisited for potential inclusion of participants with children younger than 5 years.

- **Safety Monitoring of Children in the Home**

- 1) The family will be provided with educational materials to review with their children using components of the American Veterinarian Medical Association (AVMA) Dog Bite Prevention Articles located on the AVMA website (<https://www.avma.org/public/Pages/Dog-Bite-Prevention.aspx>). Participants will also be provided with the link to the abovementioned website in order to access additional educational resources.
- 2) The dog trainer will make home visits at weeks 1 and 2 and at months 1 and 2. If, at any of these visits, the dog trainer has concerns that the dog is not comfortable in the

presence of the child, the dog will be removed from the home and the participant will be terminated from the study.

- 3) The study team, participant and her/his family will be instructed to monitor the dog's behavior regarding the dog-child interactions. In particular they will be instructed to look out for the following behaviors that may indicate the dog is stressed by the presence of the child:
- Dog actively avoids the child by hiding, moving away., etc. when child approaches
 - Dog yawn or licks lips when in the child's presence
 - Dog snaps or stares at the child
 - Dog's holds tail higher than horizontal when in child's presence
 - Dog attempts to herd child away from the veteran or other family members.
 - Dog displays other behaviors towards the child (or others) that concern the participant.

4) Participants who become pregnant or introduce a newborn, infant, or toddler into their home environment (i.e., marriage, significant other, etc.) after pairing will be provided with the "Dog Safety Education for Newborns and Infants" document (website: http://doggonessafe.com/baby_safety_around_dogs).

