If the family notices any of the above behaviors the local dog trainer or a member of the local study team must be contacted immediately. On the first report of this, the dog trainer will make a home visit to evaluate the situation. If the dog trainer has any concerns that the dog is not comfortable in the presence of the child, the dog will be removed from the home and the participant will be terminated from the study. On following reports of the same or similar behavior, the dog trainer will make a home visit on a case-by-case basis.

• Recruitment

There are three participating study sites (Portland, Iowa and Atlanta VA Medical Centers) that will focus their combined recruitment efforts on obtaining the final sample size of 220 paired participants. To reach this final sample size and control for the rate of attrition, approximately 300 participants may be consented across all of the sites.

Suggested local recruitment strategies:

1. In-services to mental health providers at clinics at the VA and surrounding Community Based Outpatient Clinics (CBOCs), and Veteran Centers and other Veteran organizations will be conducted by members of the study team using a study-approved presentation. Follow-up contacts with clinic providers will take place to answer questions that arise regarding study details. Clinicians attending the in-service presentations will be encouraged to refer Veterans they feel meet the eligibility criteria
2. Reminder emails with flier attachments sent to mental health providers.
3. Distribution of IRB approved flyers and brochures to mental health providers, directly to potential participants, placed in mental health clinic waiting areas and placed at meeting locations of veteran interest groups and organizations.

4. Vendor and other external professionals' referrals of potential participants via provision of study team contact information, IRB approved flyers/brochures and/or in-service presentation.
5. Advertising via Social media outlets (i.e., VA Facebook page, VA Twitter account), VA related newsletters (internal and external), and VA closed circuit TV. All content will be limited to language currently included in the approved study brochure and/or flyer.
6. Information booths set up at local community events with a focus on Veteran populations.

Referrals:

Potential participants can be:

- Self-referred.
- Referred by a local mental health provider via CPRS or other contact.

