Month 2 contact will take place 60 days (± 14 days) after receipt of dog. If at the month 1 post-pairing visit the dog trainer was satisfied that the Veteran and dog had bonded and that there were no concerns, this contact will be by telephone. If the dog trainer had concerns, this visit will take place in the participant's home. Further, if there is a child living in the home who is aged between 5 and 10 years, a home visit will be conducted regardless of the month 1 visit findings. The dog trainer will evaluate the behavior of the dog when the child is present preferably through direct observation. If this is not possible (child at school, or elsewhere) the participant will be thoroughly interviewed instead. Regardless of form of contact, the Dog Related Questions will be completed. If there is a home visit, the Veteran and Service/Emotional Support Dog Visit Report will also be completed. The participant will be reminded about the Veterinary Checklist if not already received. Participants will receive \$10 for their time and effort.

Post Pairing Outcome Visits

- **Months 3, 9 and 15 clinic visits and associated telephone calls:**

At months 3, 9 and 15 (± 14 days) after receipt of dog, the participant will attend a visit at the local VA study site. The C-SSRS, HERC non-VA care WPAI, and Medication Log will be completed in interview format. The WHO-DAS 2.0, PCL-5, PSQI, VR-12, PHQ-9, and DAR will be completed in pen and paper format. Participants will receive \$25 for each visit for their time and effort. Secondary contact information will be verified. At Months 03 and 09 the participant will be provided with the Veterinary Checklist packet (includes form 23). Each visit will last approximately 2 hours, with the exception of the month 15 visit which will be longer due to the additional steps listed below.

Month 15 Visit:

- CAPS will be administered.
- Veterinary Checklist packet (includes form 23) will be provided and should be completed around 17 Months.
- Discussions related to keeping or returning the study dog at the end of the study will be initiated.

Within approximately 2-weeks of each clinic visit, the dog trainer will telephone the participant to complete the Dog Related Questions form.

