- SAE monitoring: a final chart review for monitoring SAEs should be completed approximately 30 days after the completion of the 18 month visit. If an SAE is identified a final SAE form will be submitted to PPCSPCC and CIRB as required.
- All CRFs should be completed and submitted to PPCSPCC.

XI. DOG REMOVALS

- **Removal and replacement of the study dog.**

Pairings between Service Dogs/Emotional Support Dogs and study participants may fail because a bond is not established between them. Vendors are experts at matching human and animal personalities to limit the possibility that this will happen. Based on information from vendors, a bonding failure will usually occur within the first two weeks after returning home with a dog. In the case of failed bonding, a VA Dog Trainer will intervene and inform a Contracting Officer's Representative (COR), who will inform the vendor. Dogs may also develop disqualifying health or behavioral problems at any time after pairing that disrupts the pairing process. In other cases the bonding relationship may be interrupted due to short term absences by the participant (i.e., hospitalization, transitional housing, etc.) or due to the death of the original study dog in which a replacement dog may be sought.

If issues are identified that require the removal of a study dog, site staff will inform their local LSI. The LSI will work with the study Chair, the National Dog Trainer, and other leadership as needed to determine whether the dog should be temporarily or permanently removed. If the decision to temporarily remove the dog is agreed upon, the research team will assess the procedure for determining when and what constitutes resolution of the extenuating circumstances and when it would be appropriate to return the dog or offer a replacement dog.

Study leadership will maintain ongoing communication during all temporary removals to monitor the situation. Should the circumstances surrounding the temporary removal of the dog not get resolved in a reasonable amount of time - as determined by study leadership - the study dog may be permanently removed. If the dog is permanently removed with no plan for a replacement dog, the participant may be asked to continue in the study to complete follow up visits (Intent to Treat). If the participant does not want to remain in the study they will be withdrawn.

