#### 3.3 Inclusion-Exclusion Criteria

##### 3.3.1 Inclusion Criteria

- 1) Males and Females greater than 18 years of age
- 2) Referral from Mental Health provider that documents PTSD.
- 3) PTSD as a result of any trauma as determined by meeting DSM 5 diagnostic criteria.
- 4) Enrolled in mental health services at VA and has attended at least one visit in the 90 days prior to consent.
  - If individual not currently enrolled in mental health treatment decides to enroll in such then he/she may become eligible to participate in the study.
  - If individual enrolled in mental health treatment schedules and attends a mental health visit then he/she may become eligible to participate in the study.
- 5) Agrees to remain in mental health treatment throughout the duration of the study
- 6) Can adequately care for and handle the dog
  - Adequately caring for a dog requires that participants will be responsible for and able to provide food, water, protection, shelter, exercise, transportation, and treatment related to their assigned dog.
  - Adequately handling the dog means having the ability to give and reinforce obedience commands and control the dog using a leash.

- 7) Home environment is suitable for a dog.
  - If the home environment can be remedied the potential participant may become eligible to participate in the study.
  - If a participant moves home while enrolled in the study the new home must be suitable for a dog
- 8) Home environment is structurally and geographically accessible for study staff
  - If the home is geographically inaccessible to study staff and, the individual cannot remedy the situation unless he/she moves home. The study team will not encourage this. If a move takes place, it will be the individual's responsibility to re-contact the study team.
  - If the individual changes home residence while enrolled in the study, the new home must be geographically accessible to study staff. If it is inaccessible, the dog will be removed, and the individual will be withdrawn from the study.
- 9) Is willing to accept randomization outcome.
- 10) Has someone to care for the dog during extended absence of the participant.
  - If no one is available to care for the dog but the situation changes then the participant may become eligible to participate.
- 11) Others in home are agreeable to having dog
  - If others in the home are not agreeable but at a later date the situation changes, then the potential participant may become eligible to participate

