### 3.7 Follow-up

The primary objective of this study is to determine how the provision of a Service Dog or an Emotional Support Dog impacts function and quality of life for Veterans with PTSD. Primarily, the objective is to compare functioning and quality of life change, relative to baseline, over the 18-month intervention period between the two groups of Veterans with PTSD, i.e., those who receive Service Dogs and those who receive Emotional Support Dogs. The secondary outcomes in this study are: 1) a reduction in PTSD symptoms as measured by the PTSD Civilian Checklist (PCL); 2) improvement in depression as measured by the PHQ-9; 3) improvement in sleep as measured by the Pittsburg Sleep Quality Index (PSQI); 4) decreased thoughts of suicide as measured by the Columbia-Suicide Severity Rating Scale (C-SSRS); and 5) to characterize and compare how healthcare costs and utilization are impacted. All primary and secondary outcome measures will be collected at baseline, clearing, and at 3, 6, 9, 12, 15 and 18 month post-pairing. The following forms will be used during the follow-up phase of the study.

Table 2. Follow-up Phase Data Forms

Form #	FORM Name	1 week	2 week	1 month	2 month	3 month	6 month	9 month	12 month	15 month	18 month
	PHASE	2	2	3	3	3	3	3	3	3	3
	VISIT #	01	02	01	02	03	06	09	12	15	18
	LOCATION	Home	H/P	Home	H/P	Clinic	Home	Clinic	Home	Clinic	Home
3	CAPS										R
7	WHO-DAS 2.0					R	R	R	R	R	R
8	PCL-5					R	R	R	R	R	R
9	PSQI					R	R	R	R	R	R
10	VR-12					R	R	R	R	R	R
11	C-SSRS					R	R	R	R	R	R
12	PHQ-9					R	R	R	R	R	R
13	DAR					R	R	R	R	R	R
14	HERC Non-VA Utilization					R	R	R	R	R	R
15	WPAI: GHP v2.0					R	R	R	R	R	R
17	Medication Log	A	A	A	A	A	A	A	A	A	R
18	Payment Log	A	A	A	A	A	A	A	A	A	R
19	Post Pairing Evaluation	R	A	A	A	A	A	A	A	A	A
20	Veteran and Service/ES Dog Visit Report	R	A	R	A	A	R	A	R	A	R
21	Dog Related Questions	R	R	R	R	R	R	R	R	R	R
22	Dog Return	A	A	A	A	A	A	A	A	A	A
23	Veterinarian Checklist	R					R		R		R
24	Study Completion/Termination	A	A	A	A	A	A	A	A	A	R
24a/b	Exit Interview – SERV or Exit Interview – EMOT										R
24c	Dog Trainer Evaluation										R
25	Protocol Deviation	A	A	A	A	A	A	A	A	A	A
26	Adverse Events	A	A	A	A	A	A	A	A	A	A
26a	Adverse Events for Dogs	A	A	A	A	A	A	A	A	A	A
27	Serious Adverse Events	A	A	A	A	A	A	A	A	A	A
27a	Serious Adverse Events for Dogs	A	A	A	A	A	A	A	A	A	A
28	AE/SAE Follow-up	A	A	A	A	A	A	A	A	A	A
28a	SAE Follow-up for Dogs	A	A	A	A	A	A	A	A	A	A

H/P = HOME/PHONE

R = REQUIRED

A = AS NEEDED

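### Two rules end study participation when the dog is removed, and other follow-up after removal is discretionary without criteria, so outcomes are lost avoidably for intervention-related reasons

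*Protocol*

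**What the plan says.** **Mandatory termination.** Two rules tie removal of the dog to the end of participation.

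- *Child comfort* (Protocol, Safety Monitoring of Children in the Home). "The dog trainer will make home visits at weeks 1 and 2 and at months 1 and 2". If the trainer has concerns about the dog in the "presence of the child, the dog will be removed from the home and the participant will be terminated from the study". The paragraph on family reports of worrying behaviour repeats this consequence.
- *Move to an inaccessible home* (Protocol, Inclusion Criteria, item 8): "the dog will be removed and the individual will be withdrawn from the study". SAP 3.3.1 repeats the rule.

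**Discretionary follow-up.** For a permanent removal with no replacement planned, Protocol XI (Removal and replacement of the study dog) says "the participant may be asked to continue in the study to complete follow up visits (Intent to Treat"). The subsection on permanent removal says such participants may be eligible to continue. The local investigator and study leadership are consulted, and leadership can find a participant ineligible. No criteria are stated. The same subsection says follow-up data matter for the validity of the results. It sets out a clinic route at $25 per visit and shows that some participants are already being followed without a dog.

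**Who knows the arm.** Under SAP 3.4 the local investigator, study team and Chair's Office are unblinded after the home clearing visit.

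**Outcomes and analysis.** "All primary and secondary outcome measures will be collected at baseline, clearing, and at 3, 6, 9, 12, 15 and 18 month post-pairing" (SAP 3.7). ITT is everyone randomized, analysed as assigned whether or not they complete (Protocol XVIII, Statistical Methods; SAP 5.2). SAP 5.3 bases the primary analysis on observed data. It excludes data collected after a dog is replaced and does not mention data collected after permanent removal.

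**The concern.** Removing a dog ends the intervention. It does not in itself prevent a Veteran from completing questionnaires in a clinic. Where the protocol ends participation at the same moment, outcomes go missing because of an event that follows randomization and concerns the treatment itself. The optional route raises a related problem: people who know the arm decide, without written criteria, whose outcomes continue to be collected. If removals or those decisions differ between arms, and those lost differ from those kept, the comparison by assigned group could be distorted. Outcomes not collected can afterwards only be modelled.

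**Working it through.** **1. The plan's own figures.** Inputs from Protocol XVIII, Table 6: MCS mean 33.2, SD 10.6, 15% difference, two-sided 0.05, power 0.85.

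- Difference: 0.15 × 33.2 = 4.98 points.
- n per group = 2 × (1.960 + 1.036)² × 10.6² / 4.98² = 2 × 8.98 × 112.36 / 24.80 = 81.4, rounded up to 82.
- Allowing 25% loss: 82 / 0.75 = 109.3, rounded up to 110.

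Both reproduce. With 110 per arm and 25% loss, 82.5 per arm remain and power is 0.855. The SAP 3.8 fallback also reproduces: 72 / 0.80 = 90 per arm, with power 0.805 at 72. Losses under these rules are therefore budgeted for in power, provided total loss stays within the allowance. What remains is which outcomes are lost, and why.

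**2. Timing of the child-comfort rule.** The post-pairing outcome visits are months 3, 6, 9, 12, 15 and 18, which makes 6.

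- Latest in-window month 2 contact (Protocol X): 60 + 14 = day 74.
- Earliest in-window month 3 visit, taking month 3 as 90 days (an assumption, since the protocol gives months): 90 − 14 = day 76.

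The windows do not overlap. Termination at any of the four scheduled visits, if in window, leaves 0 of 6 post-pairing assessments. After a family report or a move, removal can come at any time; a participant with k assessments already done loses 6 − k, so up to 6.

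**3. The rules beside the ITT text.**

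- The ITT definitions settle who is analysed and in which arm. A terminated participant remains in the set with whatever was collected, so the definition is not breached.
- Protocol XI attaches the ITT label to follow-up after removal and treats the data as important to validity. The two mandatory rules do not mention that route, and the permissive wording does not guarantee it. The inconsistency lies here.

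**4. Possible bias, by assumption only.** No removal or post-removal termination rate is given. For a simple difference in observed means, with the same gap between missing and observed participants in both arms, bias = (difference in loss between arms) × (gap).

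- Equal loss: 0 points.
- 10 percentage points × 5 MCS points = 0.5 points, or 0.5 / 4.98 = 10% of the planned difference.
- 20 percentage points × 10 points = 2.0 points, or 40%.

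These inputs are not estimates for this trial, and the planned mixed model would not behave exactly like a raw mean.

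**The case against.** The strongest reply is that the two rules should not be read alone. Protocol XII makes case-by-case evaluation the norm for terminations and requires leadership approval. The permanent-removal subsection lists termination by staff for ineligibility among its reasons and then allows continued follow-up, so the general route arguably reaches these cases. Some listed grounds, such as deployment, incarceration or worsening health, justify discretion. The sample size allows 25% loss, and SAP 5.3 plans multiple imputation and pattern-mixture models if missingness is substantial.

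Much of this stands as mitigation. It does not supply criteria, and it does not reconcile the mandatory wording with the optional route. The loss allowance protects power, not against selective loss. After a move, distance may indeed rule out clinic visits, so the child rule is the main practical target.

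Several stronger readings are tempting but unsupported:

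- *The rules violate the ITT definition.* They do not; dropouts are expressly kept.
- *The dog-death provision (Protocol XIII) is a third mandatory rule.* It first calls for termination when no replacement is wanted, but then lets data collection continue if the participant is willing. It is clumsy, yet it already gives what is asked for here.
- *The discontinuation list in Protocol XIII is another instance.* It runs from termination to removal of the dog, the reverse of this concern.
- *Outcomes after permanent removal have no place in the analysis.* Analysis by assignment and use of observed data include them by default; only post-replacement data are excluded.
- *The 10 placements mentioned under the child exclusion show how many are affected.* That number triggers a review of the criterion. It is neither a forecast nor a removal rate.

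**Conclusion.** The point holds as an avoidable source of missing outcomes and an internal inconsistency, not as an error in the ITT definition or the sample size. Two rules mandate the end of participation at dog removal, and follow-up after other permanent removals is left to unblinded decision-makers without criteria. The only size that can be counted is per participant: all 6 post-pairing assessments are lost after termination at an in-window scheduled child-safety visit (with month 3 taken as 90 days), and up to 6 otherwise. How many participants this touches, and whether bias results or in which direction, cannot be derived. A reader might infer that the comparison is biased towards one arm; nothing in the documents supports that. The change is a cheap improvement, useful only while outcomes can still be collected.

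**What to change.** - Keep every dog-removal rule.
- In both child-comfort paragraphs, and in the inaccessible-home rule (Protocol inclusion item 8 and SAP 3.3.1) where feasible, replace termination from the study with cessation of the intervention. Table 5 already has separate forms for dog return (form 22) and study termination (form 24).
- In Protocol XI, replace the permissive wording so that every participant who has not withdrawn consent is offered the remaining outcome visits through the existing clinic route, unless a safety or feasibility reason, such as distance, is documented.
- As clarifications only, add a sentence to SAP 5.3 confirming that outcomes after permanent removal enter the ITT analysis, and tidy the dog-death wording.

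The cost is a protocol amendment with Central IRB approval, possibly revised consent wording (the consent pages were not available to check), staff time for the visits, and payments of at most 6 × $25 = $150 per participant followed. No new form is needed.
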